4.5.2 Handling of Missing Values

MMRM analyses account for missing data using 'a missing at random' assumption, i.e., there is a systematic relationship between the propensity for missing values and the observed data, but not the missing data. Under such assumptions, MMRM is shown to provide unbiased estimates of the treatment effect whilst analysis of only complete cases using analysis of covariance (ANCOVA) is biased.

As such missing values will not be imputed.

4.6 Analysis of Secondary Objectives

4.6.1 Secondary Endpoint: Specific QoL Scores

Measurements of health related QoL indicators will be evaluated using the specific QoL scores and categorized QoL scores change from baseline to each treatment day to determine the effectiveness of the two treatment groups (Daytime, Daytime+Nighttime).

The Specific QoL Scores consist of 7 separate questions on QoL, scored 0 ('not at all') to 7 ('severely'). Lower scores represent better outcomes. Each specific question covers one of the following topics:

- Social activities
- Feeling self-conscious around people
- Coughing in public
- Falling asleep
- Sleeping through the night
- Energy
- Motivation

Changes from baseline in Quality of Life (QoL) domain scores (Sleep Quality, Social Activities, Physical Activities, and Vitality) will be analyzed longitudinally using the same methodological approach as the primary outcome. The analysis will be conducted for the mITT population, with results presented in Tables 14.2.2.1.(1-2) and Figures 14.2.4.(1-2); 14.2.5.(1-2). A linear mixed-effects model for repeated measures (MMRM) will be fitted separately for each QoL domain. Each model will include treatment day as a categorical fixed effect, baseline QoL score as a continuous covariate, and a random intercept for subject to account for within-subject correlation. The models will employ an unstructured covariance matrix, Kenward-Rogers degrees of freedom adjustment, and restricted maximum likelihood estimation (REML) to ensure valid inference. For each QoL domain and treatment group, the following estimates will be reported at each timepoint: estimated mean changes from baseline with 95% confidence intervals, between-treatment differences in mean changes with 95% confidence intervals, standardized effect sizes (Cohen's d) with 95% confidence intervals, and associated p-values for treatment comparisons. Statistical significance will be evaluated at $\alpha=0.05$ level. Given the exploratory nature of the QoL analyses, p-values will be reported without adjustment for multiplicity, but interpretations will consider the potential impact of multiple testing on Type I error rates. Sensitivity analyses for the robustness of results to missing data and distributional assumptions will follow the same approach as specified for the primary outcome.

4.7 Exploratory Analyses

A Non-Common-Cold-Med (NCCM) population will include all patients in the mITT population who have not used other medicinal products which might influence reported symptom severity. Reported concurrent medications will be assessed in a Blind Data Review (BDR) meeting to identify potentially interfering medications. The NCCM population will be created, and the decision to perform analyses on this population will be made during the BDR meeting. There is no pre-defined threshold on differences between the mITT population and the NCCM population.

The NCCM population will exclude participants with potentially contraindicating medications. This population will be used for the primary and secondary endpoint analyses, and results will be presented in the same Table format as the primary and secondary endpoints, with Table numbers ended in '.2'.

4.8 End of study satisfaction survey

At the end of the study (either Day 7, or the day after the last treatment dose) subjects are asked the following question in an exit survey:

- Would you use Robitussin to treat your cough/cold again? (Y/N)

Results from these exit survey question will be summarized descriptively using frequencies and absolute percentages in Table 14.2.2.4.

4.9 Analysis of Safety

4.9.1 Adverse Events and Serious Adverse Events

All AEs will be coded using MedDRA. AEs will be categorized as related or unrelated by Lindus Health prior to database lock. The number of AEs/SAEs and the number of subjects with AEs/SAEs will be listed and tabulated.

The absolute and relative frequency of adverse events (AEs) in each group will be reported, including the total number of events, the total number of patients experiencing at least one event, and the frequency of events by severity and AE category. Safety analyses will be performed on the Safety population, according to investigational product received. AEs will be regarded as 'treatment emergent' if they occur on or after the first use of investigational product at baseline (Day 0, pre-randomization). In the event of a missing start date, an AE will be assumed to be 'treatment emergent' unless the end date is prior to starting treatment. In case of misallocation compared to the randomization schedule, TEAEs will be associated with the most recent investigational product received.

A listing of all Treatment Emergent AEs (TEAEs) will be presented for all subjects in the Safety population with the following AE summaries (number of distinct AEs and frequency/proportion of subjects affected) presented by treatment group and overall:

- TEAEs—Overview (Table 14.3.1.1)
- TEAEs by System Organ Class (SOC) and Preferred Term (PT) (Table 14.3.1.2)
- TEAE by Relationship, System Organ Class and Preferred Term (Table 14.3.1.3)
- TEAE by System Organ Class, Preferred Term and Worst Severity (Table 14.3.1.4)
- Treatment Emergent Serious Adverse Events by System Organ Class and Preferred Term (Table 14.3.1.5)

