*f* WURSS–21 to be completed at the time of Baseline/Screening to confirm eligibility as well as daily during treatment (from Day 1 up to Day 7).

*g* Study product (Robitussin) to be shipped only after screening/baseline assessments are completed and eligibility is confirmed; up to 8 days' worth of study product(s) will be shipped together to ensure there is no interruption in study timeline or treatment duration.

*h* Participant will complete an eDiary documenting Robitussin use each day directly through the Citrus ePRO module.

*i* Participant-reported End of Study Survey will be completed at the end of study directly through the Citrus ePRO module. Participants ending product use early will complete the survey one day after their last reported dose; participants dosing on Day 7 will complete the survey on Day 7.

*j* Participant-reported Change in Health will be recorded two days after last study product administration.

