#### 5.4.5 Randomization

If the subject successfully meets eligibility criteria, the subject will be considered enrolled. At enrollment, the following activities will occur:

- The subject will move forward to randomization into one of two study groups (on a 1:1 allocation) as follows:
  - Group 1: will be instructed to take the following per label instructions for up to 8 days or until resolution of symptoms, whichever occurs first:

Product	Dose
Robitussin Maximum Strength Cough and Chest Congestion DM	Up to 20 ml*
*Not to exceed 6 doses in any 24 hour period.	

- Group 2: will be instructed to take the following per label instructions for up to 8 days or until resolution of symptoms, whichever occurs first:

Product	Dose
Robitussin Maximum Strength Cough and Chest Congestion DM	Up to 20 ml*
Robitussin Maximum Strength Nighttime Cough DM	Up to 20 ml*
*Not to exceed 4 doses of daytime + 1 dose of nighttime OR 3 doses of daytime + 2 doses of nighttime in any 24 hour period.	

- Upon group allocation, study team will arrange delivery of the study product(s).

- Once the delivery is successfully received, the subject will confirm receipt and usability of the product(s) via an online questionnaire directly entered into the EDC platform.
  - If unsuccessful (e.g. lost, damaged) study team will discuss with participant and arrange a new delivery if needed.

During the screening visit, subjects will be provided with dosing instructions and training on how to complete the assessment, questionnaires, and eDiaries. Subjects will be reminded to reach out to the study team with any questions or concerns.

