7.1 Study Product Supplies

Each subject will receive sufficient study product(s) to cover usage during the treatment period of the study. The following study products will be supplied by the CRO’s preferred vendor ([Table 7-1](#)). Study product(s) usage instructions are consistent with the commercially available pack instructions. Subjects will not be required to return or destroy used/unused study products after treatment discontinuation, completion of study or withdrawal.

Table 7-1 Investigational/Study Product Supplies

	Group 1	Group 2 (Product 1 + Product2)
Product Name	Robitussin Maximum Strength Cough and Chest Congestion DM	Robitussin Maximum Strength Cough and Chest Congestion DM  Robitussin Maximum Strength Nighttime Cough DM
Pack Design	Labeled commercial pack	Labeled commercial pack
Dispensing Details	Shipped to subject upon randomization	Shipped to subject upon randomization
Haleon formula codes:	CCI	CCI
Dose and usage Instructions	Up to 20 ml, not to exceed 6 doses in any 24-hour period.	Up to 20 ml per dose. Not to exceed 4 doses of daytime + 1 dose of nighttime

		OR 3 doses of daytime + 2 doses of nighttime in any 24-hour period.
Route of Administration	Oral	Oral
Return Requirements	All unused/used study products will not be returned	All unused/used study products will not be returned

\*See dosing instructions in [Section 5.4.5](#)

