## 7.2 Product Supplies, Product Storage, Accountability, Returns and Destruction

Study products are to be dispensed only to subjects enrolled in the study in accordance with the protocol, by delegated study staff. Enrolled/randomized subjects will be informed on product usage and storage and what to do in the event of product loss when the products are first dispensed.

All study products supplied are for use only in this clinical study and should not be used for any other purpose.

Orders for study product(s) are to be placed immediately following randomization for delivery to subjects. Given this delivery model and the shelf stability of the product(s), a formal accountability form/record will not be maintained, however trained study staff will maintain an order and delivery tracker.

At the end of the study, subjects may retain any remaining/unused study product(s).

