## **8.3 Statistical Analyses**

Additional details of the proposed statistical analysis will be documented in the statistical analysis plan (SAP), which will be written following finalization of the protocol and prior to study data analysis. All analyses will be carried out and reported without adjusting for multiple comparisons, reporting nominal p-values.

Each of the treatment groups will be analyzed separately for all endpoints; there is no comparison between the study groups (daytime product only and daytime/nighttime product combination).

Baseline WURSS-21 and the Specific QoL questions are completed at the Virtual Visit, prior to study product(s) shipment to the subject.

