### 9.3 Time Period and Frequency for Collecting AE and SAE Information

All AEs, and therefore all SAEs (except from those exempt from recording, as described in section 9.1 and section 9.2) will be collected from immediately after a subject is randomized within the trial and until 2 days following the last administration of study product.

A change in health survey will be released to subjects 2 days after their last study product(s) dose. If a subject reports a change in health, a member of the study team will reach out to record the relevant details.

Medical occurrences that began before randomisation will be recorded in the Medical History/Current Medical Conditions section of the Electronic Case Report Form (eCRF), not the AE section.

Details recorded by the subject that meet the definition of a serious AE must be discussed with the subjects and transcribed into the SAE section of the eCRF

All SAEs will be recorded and reported to the sponsor or designee immediately, and under no circumstance should this exceed 24 hours. The investigator will submit updated SAE data to the sponsor within 24 hours of it being available.

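### SAP 4.9.1 describes first product use as happening at baseline before randomization, which contradicts the protocol's randomize-then-ship order and leaves the treatment-emergent reference date ambiguous

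*SAP*

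**What the plan says.** SAP 4.9.1 treats adverse events as treatment-emergent "if they occur on or after the first use of investigational product at baseline (Day 0, pre-randomization"). An event with no start date is assumed treatment-emergent unless it ended before treatment began. Five summary tables (14.3.1.1 to 14.3.1.5) rest on this definition. SAP Appendix 1 marks the overview and the summary by system organ class and preferred term as topline.

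The protocol sets out the order of events in several places:

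- Protocol 8.3: "Baseline WURSS-21 and the Specific QoL questions are completed at the Virtual Visit, prior to study product(s) shipment to the subject".
- Protocol 7.2: "Orders for study product(s) are to be placed immediately following randomization for delivery to subjects".
- Protocol Table 7-1, dispensing row: "Shipped to subject upon randomization".
- Protocol Table 5-1, footnote g: "Study product (Robitussin) to be shipped only after screening/baseline assessments are completed and eligibility is confirmed".
- Protocol 9.3: AEs and SAEs "will be collected from immediately after a subject is randomized within the trial". Anything that began earlier goes to medical history.

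The safety endpoint (Protocol Table 2-1, SAP 1.2) is the number and percent of patients reporting AEs or SAEs while on treatment.

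**The concern.** A treatment-emergent rule needs one reference date per subject. This sentence gives two that can differ. One is first use of the product. The other is baseline, Day 0, before randomization.

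The second is not an idle phrase, because the SAP gives those words a fixed meaning. Its Table 1 heads the visit column Day 0 (Baseline), 4.5.1.1 equates baseline with Day 0, and 3.1 places baseline in screening and enrolment. A programmer following the SAP's own terms could reasonably set the anchor to the baseline visit date.

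What is at stake is whether an event that started while the subject was waiting for the parcel appears in tables meant to describe events on treatment.

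**Working it through.** The plan states no figure on this point, so there is nothing to reproduce. The check sets the SAP rule against the protocol's sequence and then classifies events under each reading.

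**Sequence under the protocol** (5.4, 5.4.5, 7.1, 7.2, 8.3, 9.3)

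1. Baseline WURSS-21 and specific QoL questions at the virtual visit; eligibility confirmed.
2. Randomization (Day 0 in Table 5-1). AE collection opens.
3. Product ordered and shipped.
4. Subject confirms receipt; a lost or damaged parcel may be re-sent.
5. First use.

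Step 5 cannot come before step 2, so first use before randomization is impossible. First use on Day 0 *after* randomization is possible. Table 5-1 marks product use and the usage eDiary on Day 0, its footnote a allows for same-day receipt, and Protocol 5.6 runs treatment from Day 0 to Day 7.

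**Two readings of the SAP rule**

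- Reading A: the anchor is the actual first use, and the parenthetical is ignored.
- Reading B: the anchor is Day 0, before randomization.

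| Onset of event | Reading A | Reading B |
|---|---|---|
| Before randomization | Medical history, not an AE | Medical history, not an AE |
| After randomization, before first use | Not treatment-emergent | Treatment-emergent |
| At or after first use | Treatment-emergent | Treatment-emergent |
| Start date missing, ended before first use | Not treatment-emergent | Treatment-emergent, if treatment start is also taken as Day 0 |
| Start date missing, ended at or after first use | Treatment-emergent | Treatment-emergent |

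The readings differ only for events whose onset or end falls between randomization and first use. Those are also the only dated AEs that the start of the window can ever exclude, since nothing earlier is recorded as an AE. Under Reading B the rule therefore excludes no recorded AE, and treatment-emergent becomes the same as recorded in a subject who used product.

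**Size of the exposed gap**

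- Product received and first used on Day 0: the gap is under one day. If only dates are held, both readings classify identically.
- Later receipt: the gap is the transit time, plus any re-delivery and any delay by the subject before first use. Neither document gives a delivery time, so no upper limit can be set.
- Subjects who never use product are outside the Safety population (SAP 4.2.3) and do not enter the tables under either reading.

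**The case against.** The strongest defence is that the operative words key on first use. The missing-date sentence that follows tests against treatment start, and SAP 4.4.2 defines prior and concomitant medications by first use and lists days relative to a study product start date. On that view the parenthetical is a slip, and a sensible programmer would use first use. This is fair as far as it goes, and it is why misclassification is a possibility and not a certainty. It does not remove the contradiction: the sentence still describes first use as occurring at a time when it cannot occur.

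Three stronger readings are tempting, and the documents do not support them.

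- *A reader might infer that pre-dose events will be counted as treatment-emergent.* That follows only under Reading B. Under Reading A every dated pre-dose event is excluded.
- *A reader might infer that the tables will fill with untreated cold symptoms.* Protocol 5.8 and Section 9 say that reports on the WURSS-21 symptom domain are not AEs. Protocol 9.1 excludes expected signs and symptoms of the studied condition unless they are more severe than expected.
- *A reader might try to size the effect as a share of the window.* Day 0 to Day 9 at the latest (Protocol 5.6) is 10 days, so an assumed delivery wait of 0 to 3 days gives 0/10 to 3/10, or 0% to 30%. The wait is assumed, and the result is a share of calendar days, not of events. The scheduled AE check in Table 5-1 begins on Day 1, although 9.3 opens collection at randomization and 9.5 lets subjects report at any time.

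It is also true that the safety output is descriptive, with no planned test, so no inference depends on this date.

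**Conclusion.** The definition is wrong as written. First use before randomization contradicts Protocol 5.4.5, 7.1, 7.2 and 8.3, and the sentence leaves the reference date for all five treatment-emergent tables open to two readings. If Day 0 before randomization is programmed, AEs between randomization and first use could be counted as treatment-emergent, and the start of the window would exclude no recorded AE.

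The number of events affected cannot be given, because delivery time is not stated. It is probably small: the exposure is confined to that gap, disappears by date for subjects who first use product on Day 0, and does not extend to ordinary cold symptoms. The conclusion that the text is contradictory rests on no assumption. The misclassification rests on the parenthetical being programmed as the anchor and on some subjects first using product after Day 0.

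**What to change.** In SAP 4.9.1:

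1. Delete the words that place first use at baseline, Day 0, before randomization.
2. Define an AE as treatment-emergent if its onset is on or after the recorded date of first study product use, with time if time is collected. Use the same study product start date as SAP 4.4.2, and tie the missing-start-date rule to it.
3. State how an event with onset on the first-use date is classified when no time is available. The eDiary items listed in Protocol 5.5 are product type and number of doses, so the rule should not depend on a clock time. Counting such events as treatment-emergent would match the existing missing-date convention.
4. In the planned all-AE listing (16.2.7.1), show events between randomization and first use as non-treatment-emergent, so that they stay visible.

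The cost is a sentence or two in the SAP and one flag. The daily usage eDiary runs from Day 0, and the SAP already plans a product start date, so no new data are needed.

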4.10 Analysis of Other Variables

Not applicable.

5 Changes to the Protocol Defined Statistical Analysis Plan

Rules to halt diary entries being sent out were not in place for all participants and therefore a subset of participants will have reported outcome and compliance data after they responded

that they had stopped study treatment. To highlight this, the data exports will be flagged under the variable QSSPID, with each issue noted.

Data flagged in the QSSPID variable will be excluded from all analysis tables and aggregated data. However, this data will be available in all relevant listings, with the QSSPID flag visible for each relevant participant. Information about how the flagged data will be excluded from the analysis datasets will be available in the analysis dataset specifications.

6 References

FDA, Considerations for the Use of Real-World Data and Real-World Evidence to Support Regulatory Decision-Making for Drug and Biological Products (Aug. 2023), <https://www.fda.gov/media/171667/download>.

Appendix 1: List of Data Displays

CSR Section	TLF	Number	Title	Population	Topline
14.1 Demographic Data, Subject Disposition and Subject Characteristics Summary Tables and Figures					
	Table	14.1.1	Subject Disposition Incidence of Protocol Deviations	All Screened Subjects	T
	Table	14.1.2	Demographic and Characteristics	All Randomized Subjects	
	Table	14.1.3	Summary of Medical History	Safety Population	T
	Table	14.1.4	Summary of Concomitant Medications	Safety Population	
	Table	14.1.5	Summary of Product Compliance	Safety Population	
	Table	14.1.6	Summary of Daily Product Use	Safety Population	
	Table	14.1.7			
14.2 Primary and Secondary Endpoint Summary Tables and Figures					
	Table	14.2.1.1.1	Primary Endpoint: Summary and Statistical Analysis of WURSS-21 Total Scores	mITT Populaton	T
	Table	14.2.1.1.2	Primary Endpoint: Summary and Statistical Analysis of WURSS-21 Total Scores	NCCM Populaton	
	Table	14.2.1.2.1	Primary Endpoint: Summary and Statistical Analysis of WURSS-21 Total Symptom Domain	mITT Population	T
	Table	14.2.1.2.2	Primary Endpoint: Summary and Statistical Analysis of WURSS-21 Total Symptom Domain	NCCM Population	

CSR Section	TLF	Number	Title	Population	Topline
	Table	14.2.1.3.1	Primary Endpoint: Summary and Statistical Analysis of WURSS-21 Total QoL Domain	mITT Population	T
	Table	14.2.1.3.2	Primary Endpoint: Summary and Statistical Analysis of WURSS-21 Total QoL Domain	NCCM Population	
	Table	14.2.1.4.1	Primary Endpoint: Summary and Statistical Analysis of WURSS-21 Individual Symptom Domains	mITT Population	T (cough symptom only)
	Table	14.2.1.4.2	Primary Endpoint: Summary and Statistical Analysis of WURSS-21 Individual Symptom Domains	NCCM Population	
	Table	14.2.1.5.1	Primary Endpoint: Summary and Statistical Analysis of WURSS-21 Individual QoL Domains	mITT Population	T
	Table	14.2.1.5.2	Primary Endpoint: Summary and Statistical Analysis of WURSS-21 Individual QoL Domains	NCCM Population	
	Table	14.2.2.1.1	Secondary Endpoint: Summary and Statistical Analysis of Specific QoL questions	mITT population	T
	Table	14.2.2.1.2	Secondary Endpoint: Summary and Statistical Analysis of Specific QoL questions	NCCM population	
	Table	14.2.2.2.1	Secondary Endpoint: Summary and Statistical Analysis of Categorized QoL factors	mITT population	

CSR Section	TLF	Number	Title	Population	Topline
	Table	14.2.2.2.2	Secondary Endpoint: Summary and Statistical Analysis of Categorized QoL factors	NCCM population	
	Table	14.2.2.3.1	Summary of Secondary Endpoint (effect of Robitussin on specific QoL questions)	mITT Population	
	Table	14.2.2.3.2	Summary of Secondary Endpoint (effect of Robitussin on specific QoL questions)	NCCM Population	
	Figure	14.2.3.1	Summary WURSS-21 Total Score	mITT Population	
	Figure	14.2.3.2	Summary WURSS-21 Total Score	NCCM Population	
	Figure	14.2.4.1	Summary of WURSS-21 Total Symptom Domain	mITT Population	
	Figure	14.2.4.2	Summary of WURSS-21 Total Symptom Domain	NCCM Population	
	Figure	14.2.5.1	Summary of WURSS-21 Total QoL Domain	mITT Population	
	Figure	14.2.5.2	Summary of WURSS-21 Total QoL Domain	NCCM Population	
	Figure	14.2.6.1	Summary of WURSS-21 Question 7 (Cough)	mITT Population	
	Figure	14.2.6.2	Summary of WURSS-21 Question 7 (Cough)	NCCM Population	
	Table	14.2.2.4	Summary of End of Study Questionnaire	Safety Population	
